10.3.5. Recording and Follow-Up of AE and/or SAE

AE and SAE Recording
 
When an AE/SAE occurs, it is the responsibility of the Investigator to review all documentation (e.g., hospital progress notes, laboratory reports, and diagnostics reports) related to the event.The Investigator will then record all relevant AE/SAE information in the eCRF.It is not acceptable for the Investigator to send photocopies of the subject's medical records to the Medical Monitor (or designee) in lieu of completion of the AE/SAE eCRF page.There may be instances when copies of medical records for certain cases are requested by the Medical Monitor (or designee). In this case, all subject identifiers, with the exception of the subject number, will be redacted on the copies of the medical records before submission to the Medical Monitor (or designee).The Investigator will attempt to establish a diagnosis of the event based on signs, symptoms, and/or other clinical information. Whenever possible, the diagnosis (not the individual signs/symptoms) will be documented as the AE/SAE.

Assessment of Intensity
 
The severity of each AE will be assessed at onset by a nurse and/or physician. When recording the outcome of the AE the maximum severity of the AE experienced will also be recorded. The severity of the AE will be graded according to the CTCAE v5.0:
 
Grade 1: Mild; asymptomatic or mild symptoms; clinical or diagnostic observations only; intervention not indicated.
 
Grade 2: Moderate; minimal, local, or noninvasive intervention indicated; limiting age-appropriate instrumental Activities of Daily Living (ADL)*.
 
Grade 3: Severe or medically significant but not immediately life-threatening; hospitalization or prolongation of hospitalization indicated; disabling; limiting self-care ADL**.
 
Grade 4: Life-threatening consequences; urgent intervention indicated.
 
Grade 5: Death related to AE.
 
ADL:
 
*Instrumental ADL refer to preparing meals, shopping for groceries or clothes, using the telephone, managing money, etc.

AE and SAE Recording

**Self-care ADL refer to bathing, dressing and undressing, feeding self, using the toilet, taking medications, and not bedridden.

Assessment of Causality

The Investigator is obligated to assess the relationship between IP and each occurrence of each AE/SAE.

- A ““reasonable possibility”” of a relationship conveys that there are facts, evidence, and/or arguments to suggest a causal relationship, rather than a relationship cannot be ruled out.
- The Investigator will use clinical judgment to determine the relationship.
- Alternative causes, such as underlying disease(s), concomitant therapy, and other risk factors, as well as the temporal relationship of the event to IP administration will be considered and investigated.
- The Investigator will also consult the Investigator’s Brochure (IB) and/or Product Information, for marketed products, in his/her assessment.
- For each AE/SAE, the Investigator **must** document in the medical notes that he/she has reviewed the AE/SAE and has provided an assessment of causality.
- There may be situations in which an SAE has occurred and the Investigator has minimal information to include in the initial report to the Medical Monitor (or designee). However, **it is very important that the Investigator always make an assessment of causality for every event before the initial transmission of the SAE data to the Medical Monitor (or designee)**.
- The Investigator may change his/her opinion of causality in light of follow-up information and send an SAE follow-up report with the updated causality assessment.
- The causality assessment is one of the criteria used when determining regulatory reporting requirements.

Causality Categories:

- **Related** – The AE is known to occur with the IP, there is a reasonable possibility that the IP caused the AE, or there is a temporal relationship between the IP and event. Reasonable possibility means that there is evidence to suggest a causal relationship between the IP and the AE.
- **Not Related** – There is not a reasonable possibility that the administration of the IP caused the event, there is no temporal relationship between the IP and event onset, or an alternative etiology has been established.

AE and SAE Recording
Follow-up of AEs and SAEs

• The Investigator is obligated to perform or arrange for the conduct of supplemental measurements and/or evaluations as medically indicated or as requested by the Medical Monitor (or designee) to elucidate the nature and/or causality of the AE or SAE as fully as possible. This may include additional laboratory tests or investigations, histopathological examinations, or consultation with other health care professionals.• If a subject dies during participation in the study or during a recognized follow-up period, the Investigator will provide the Medical Monitor (or designee) with a copy of any post-mortem findings including histopathology.• New or updated information will be recorded in the originally completed eCRF.• The Investigator will submit any updated SAE data to the Sponsor within 24 hours of receipt of the information.

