7. DISCONTINUATION OF IP AND SUBJECT DISCONTINUATION/WITHDRAWAL

7.1. Discontinuation of Investigational Product and Subject Withdrawal from the Study

In some instances, it may be necessary for a subject to permanently discontinue IP. Temporary IP interruption may be allowed if Investigator and Medical Monitor (or designee) assess that IP rechallenge is safe and appropriate.

Permanent discontinuation of IP at any time during the study does not mean withdrawal from the study, and the subject will be encouraged to remain in the study, complete the Early Termination (ET) visit at the time of IP discontinuation and continue to complete remaining study period during the Main Study or the Extension Study as appropriate (i.e., subjects who ET before Week 24 may complete study visits through Week 24 and subjects who ET after Week 24 may complete visits through Week 48). Procedures for the remaining visits will include assessment of AEs and updating concomitant medications. Subjects who permanently discontinue IP at or after Week 16 and before Week 24 of the Main study will be requested to provide a liver biopsy at ET visit. (Section 1.3).

Subjects who experience clinically significant TEAEs that are assessed as a potential risk to subject safety will be discontinued from IP and undergo an ET visit as specified in the SoA. The decision to discontinue IP will be made by the Investigator and should be discussed with the Medical Monitor (or designee). If any subject experiences a Grade 3 TEAE that is considered related to IP, the Investigator should discuss treatment discontinuation with the Medical Monitor (or designee).

Subjects have the right to withdraw from the study at any time and for any reason without prejudice to their future medical care by the Investigator or at the institution. The reason for subject withdrawal from the study will be recorded in the eCRF. At the time of withdrawal from the study, the ET visit should be conducted as shown in the SoA.

A subject may discontinue IP or withdraw from the study for the following reasons:

- Adverse event
- Death
- Lack of efficacy
- Lost to follow-up
- Non-compliance with study drug
- Physician decision
- Pregnancy
- Protocol deviation
- Site terminated by Sponsor
- Study terminated by Sponsor

- Withdrawal by subject
- Randomized by mistake

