10.3.1. Definition of AE

AE Definition

• An AE is any untoward medical occurrence in a clinical study subject, temporally associated with the use of IP, whether or not considered related to the IP.• NOTE: An AE can, therefore, be any unfavorable and unintended sign (including an abnormal laboratory finding), symptom, or disease (new or exacerbated) temporally associated with the use of IP.

Events Meeting the AE Definition

• Any abnormal laboratory test results (hematology, clinical chemistry, or urinalysis) or other safety assessments (e.g., ECG, radiological scans, vital signs measurements), including those that worsen from baseline, considered clinically significant in the medical and scientific judgment of the Investigator (i.e., not related to progression of underlying disease). A clinically significant abnormality is a confirmed abnormality (by repeat testing) that is changed sufficiently from Baseline so that in the judgment of the Investigator a change in management is warranted. This alteration may include: monitoring the laboratory test further, initiating other diagnostic tests or procedures, changing ongoing treatment, or administering new treatment.• Exacerbation of a chronic or intermittent pre-existing condition including either an increase in frequency and/or intensity of the condition.• New conditions detected or diagnosed after IP administration even though it may have been present before the start of the study.• Signs, symptoms, or the clinical sequelae of a suspected drug-drug interaction.• Signs, symptoms, or the clinical sequelae of a suspected overdose of either IP or a concomitant medication. Overdose per se will not be reported as an AE/SAE unless it is an intentional overdose taken with possible suicidal/self-harming intent. Such overdoses should be reported regardless of sequelae.

Events NOT Meeting the AE Definition

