10.3.2. Definition of Suspected and Unsuspected Adverse Reaction

Suspected adverse reactions are defined as:

- Any AE for which there is a reasonable possibility that the IP caused the AE. For the purposes of Sponsor regulatory safety reporting, “reasonable possibility” means there is evidence to suggest a causal relationship between the IP and the AE. A suspected adverse reaction implies a lesser degree of certainty about causality than adverse reaction, which means any AE caused by an IP.

Unexpected AEs are defined as:

- AE which is not listed in the IB of the IP or is not listed at the specificity or severity that has been observed.

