4.1.5. Safety Endpoints

- Frequency and severity of TEAEs and SAEs
- Number of subjects who discontinued due to TEAEs and due to related TEAEs
- Incidence and shifts of clinically significant physical examination findings, ECG data and laboratory abnormalities; safety laboratory evaluations include hematology, blood biochemistry and urinalysis, serum, salivary, and urinary cortisol as appropriate
- Change from baseline in
 - Insulin-like growth factor 1 (IGF-1)
 - Bone biomarkers: Carboxy-terminal collagen crosslinks (CTX), N-terminal propeptide of type 1 collagen (P1NP) and osteocalcin
 - Thyroid stimulating hormone (TSH)
- Absolute and % change from baseline in lumbar spine, total hip, and femoral neck bone mineral density (BMD) as assessed by dual X-ray absorptiometry (DXA)
- Incidence and characteristics of anti-drug antibodies (ADA) and neutralizing antibody (NAb) after dosing (e.g., titer and binding specificity, to the FGF21 and polyethylene glycol [PEG] part of pegozafermin)
- Impact of the presence of ADAs on serum pegozafermin concentrations and clinical safety

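### The two causality categories in Protocol 10.3.5 overlap, with no rule for choosing between them, so related-AE results depend on which criterion a site applies

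*Protocol*

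**What the plan says.** The Causality Categories in Protocol 10.3.5 give three ways to be Related. The event is a recognised effect of the product, or "there is a reasonable possibility that the IP caused the AE, or there is a temporal relationship between the IP and event". They give three ways to be Not Related. A reasonable possibility is absent, or "there is no temporal relationship between the IP and event onset, or an alternative etiology has been established". No sentence says what to do when an event fits both.

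Three other statements bear on the meaning:

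- Protocol 10.3.5, just before the categories, says a reasonable possibility "conveys that there are facts, evidence, and/or arguments to suggest a causal relationship, rather than a relationship cannot be ruled out".
- Protocol 10.3.2 defines a suspected adverse reaction as "Any AE for which there is a reasonable possibility that the IP caused the AE". For the sponsor's regulatory reporting it adds that reasonable possibility "means there is evidence to suggest a causal relationship between the IP and the AE". Timing is not a separate route.
- Protocol 10.3.1 builds timing into the definition of an AE, in a sentence that closes by naming the product: "An AE is any untoward medical occurrence in a clinical study subject, temporally associated with the use of IP, whether or not considered related to".

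Relatedness is then used downstream. SAP 4.1.5 lists the endpoint "Number of subjects who discontinued due to TEAEs and due to related TEAEs", and SAP 4.2.3 repeats it for the Extension. SAP 7.10.1 tabulates related TEAEs and related serious AEs, and SAP 7.12.1 repeats those tables at the final analysis. Protocol 7.1 calls for a conversation with the Medical Monitor: "If any subject experiences a Grade 3 TEAE that is considered related to IP, the Investigator should discuss treatment discontinuation". Protocol 8.3 attaches a follow-up duty to related AEs. The SAP does not redefine relatedness. SAP 6.1.3 counts a missing assessment as related.

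**The concern.** A two-category scale works only if every event falls in exactly one category. Here two investigators with the same facts can record opposite answers and both comply. Take, as an example, laboratory-confirmed influenza three days after an injection. It is Related by timing and Not Related by established cause.

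The timing criterion raises a second problem. If timing is already part of being an AE, it cannot also separate related AEs from the rest. Sites that lean on it would record as related many events for which there is no evidence of causation. In a placebo-controlled comparison this pulls the related-TEAE rows toward the all-TEAE rows. Sites that lean on the Not Related criteria would do the opposite, so the rows would mix two standards.

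**Working it through.** The plan states no figure on this point, so there is none to reproduce. The check treats the two definitions as logical statements.

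**Inputs (Protocol 10.3.5).** Four yes/no attributes of an AE:

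- K: recognised effect of the product
- R: reasonable possibility of causation
- T: temporal relationship to the product
- A: another cause established

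**Formulas, as written.**

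- Related = K or R or T
- Not Related = (not R) or (not T) or A

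**Counting over 2 × 2 × 2 × 2 = 16 combinations.**

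- Related fails only when K = R = T = 0, with A free: 2 combinations. These are Not Related only.
- Not Related fails only when R = 1, T = 1 and A = 0, with K free: 2 combinations. These are Related only.
- The remaining 16 − 2 − 2 = 12 meet both definitions. None meets neither.

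**With a temporal relationship present (T = 1), 8 combinations.**

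| Subset | Combinations | Related | Not Related | Both |
|---|---|---|---|---|
| All T = 1 | 8 | 8 | 6 | 6 |
| T = 1, other cause established (A = 1) | 4 | 4 | 4 | 4 |
| T = 1, no reasonable possibility (R = 0) | 4 | 4 | 4 | 4 |

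Once timing is granted, no combination is Not Related only. The 2 unambiguous ones have a reasonable possibility and no established other cause.

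**Consistency with the other sections.** Take T = 1 and K = R = A = 0, an event supported by timing and nothing else. Under 10.3.5 it is Related by the timing criterion and Not Related because R = 0. Under 10.3.2 it is not a suspected adverse reaction, because that needs R = 1. The same section of 10.3.5 also says that failing to exclude a link is not enough for a reasonable possibility, yet timing alone is made enough for Related.

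**Testing possible repairs.**

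- Remove only the timing criterion: Related = K or R. This fails in 4 combinations (K = R = 0), and Not Related still fails in 2 others. Overlap is 16 − 4 − 2 = 10.
- Related = R and Not Related = not R: overlap 0 of 16, with none left unclassified.

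These counts give every combination equal weight, including some that would be rare, such as R = 1 with T = 0. They describe the wording and say nothing about how often AEs of each kind occur.

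**The case against.** The strongest reply is that 10.3.5 is not meant to be applied mechanically. It tells the investigator to use clinical judgment and to look at timing together with other causes. Temporal relationship is undefined and could mean plausible timing. That reading also fits 10.3.1 better, since that section separates being an AE from being related. Investigators and sites stay blinded to drug or placebo, so misclassification would not be driven by known assignment. Counting missing relatedness as related suggests that leaning toward Related is partly deliberate.

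Much of this limits the point, and four stronger inferences fall:

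- A reader might infer that nearly every TEAE will be recorded as Related. The literal words allow it, but the section also requires judgment, so no rate can be forecast.
- A reader might infer that a real difference between arms is hidden. SAP 7.10.1 tabulates all TEAEs, all serious TEAEs, worst grade and TEAEs leading to discontinuation by arm regardless of attribution. The endpoint in SAP 4.1.5 puts the all-cause discontinuation count beside the related one.
- A reader might infer that expedited reporting is corrupted. Protocol 10.3.2 gives sponsor reporting its own evidence standard, and 10.3.5 makes the investigator's assessment only one criterion among several.
- A reader might infer that any possible other cause makes an AE Not Related. The text requires that cause to be established.

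The Grade 3 consequence is also modest, since Protocol 7.1 asks only for a discussion.

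The reply does not cure the overlap. Judgment needs a rule to apply, and here either answer complies. The instruction to weigh timing is itself at odds with a category that makes timing sufficient.

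**Conclusion.** The defect is real and limited. As written, the Protocol 10.3.5 categories overlap in 12 of 16 logical combinations, and in 6 of the 8 where the event has a temporal relationship to the product, with no rule to settle the choice. The timing criterion conflicts with the evidence standard in 10.3.5 itself and in 10.3.2.

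The affected items are those that rest on relatedness: discontinuations due to related TEAEs in both study parts, the related-TEAE and related-SAE tables, and the Grade 3 related-TEAE discussion. They can be inconsistent between sites and diluted toward the all-TEAE comparison. The documents contain no incidence or attribution data, so the amount cannot be estimated. The all-TEAE and all-SAE tables are untouched, and so is the Extension primary endpoint in SAP 4.2.1 (frequency and severity of TEAEs and SAEs).

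This rests on reading both lists as alternatives, which is how they are punctuated, and on there being no tie-break in a document not available here, such as CRF instructions. It should be corrected, but it does not threaten the trial's main safety conclusions.

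**What to change.** Adopt the following as one change to Protocol 10.3.5:

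1. Related: there is a reasonable possibility, in the 10.3.2 sense, that the product caused the event.
2. Not Related: there is no such reasonable possibility.
3. Timing, known effects of the product and other causes are factors the investigator weighs in reaching that answer. None decides it alone.
4. Exactly one category is recorded for each AE.

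Deleting the timing criterion by itself is not enough, as the working shows.

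The cost is a wording change and a site notice. No visit, sample size or analysis method changes. The larger cost concerns AEs already recorded. SAP 3.3 shows randomization under way before April 2022, and SAP 1 cites a protocol of December 2022 and a CRF of January 2023, so events have been classified under the present wording. Either query those AEs, closed as well as open, or flag them in the related-AE tables so that the two standards are visible.

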10.3.6. Reporting of SAEs

Reporting of SAEs will be done using paper methods.

SAE Reporting to the Medical Monitor (or designee) via Paper CRF

• Facsimile or email transmission of the SAE paper CRF is the preferred method to transmit this information to the Medical Monitor (or designee).• In rare circumstances and in the absence of facsimile or email equipment, notification by telephone is acceptable with a copy of the SAE data collection tool sent by overnight mail or courier service.• Initial notification via telephone does not replace the need for the Investigator to complete and sign the SAE CRF pages within the designated reporting time frames.• Contacts for SAE reporting can be found in the relevant manual.

10.4. Appendix 4: Contraceptive Guidance and Collection of Pregnancy Information

Definitions:

Woman of Childbearing Potential (WOCBP)

Women who do not meet criteria for “females not of childbearing potential” (see below) and are post-menarche are considered to be “females of childbearing potential” in this study.

Women NOT of childbearing potential

1. Pre-menarchal
2. Surgically sterile (hysterectomy, bilateral salpingectomy, and/or bilateral oophorectomy, or bilateral tubal occlusion)
3. Postmenopausal (defined as cessation of regular menstrual periods for at least 12 months without an alternative medical cause in women over the age of 45).
 - a. In women under the age of 45 who have amenorrhea >12 months, menopausal status may be confirmed by follicle stimulating hormone (FSH) level of ≥ 30.0 mIU/mL in women not using hormonal contraception or hormone replacement therapy. Note that FSH levels can be normal or in the postmenopausal range depending on degree of ovarian dysfunction in women under 45 years of age with <12 months amenorrhea. Consult with the Medical Monitor (or designee) regarding subjects whose menopausal status may be in transition or unclear.
4. For individuals with permanent infertility due to an alternative medical cause (e.g., Mullerian agenesis, androgen insensitivity), Investigator discretion should be applied to determining study entry.

Male subjects

Men will not be required to use contraception when sexually active with a woman who is not of childbearing potential.

Men who are sexually active with WOCBP need to confirm that they will use 2 forms of contraception as per protocol.

Men who are sexually active with a partner who is pregnant are required to use a condom.

Contraception Guidance:

Contraceptive use by men or women should be consistent with local regulations regarding the methods of contraception for those participating in clinical studies.

Subjects should use highly effective, double contraception (both male and female partners) during the study and 30 days after the last dose of IP.

Double contraception is defined as a condom with one of any of the following:

- Oral contraceptive pills
- Depot or injectable birth control
- Intrauterine device (IUD)

- Contraceptive patch (e.g., Xulane®) or NuvaRing®
- Vasectomy

Subjects may not donate sperm or oocytes during the study and for 30 days or 5 half-lives (whichever is longer) after last dose of IP.

Rhythm methods are not considered as highly effective methods of birth control. Subject abstinence for the duration of the study and 30 days or 5 half-lives (whichever is longer) after last dose of IP is acceptable if it is the subject's regular practice.

Collection of Pregnancy Information

Male subjects with partners who become pregnant

- The Investigator will attempt to collect pregnancy information on any male subject's female partner who becomes pregnant while the male subject is in this study.
- After obtaining the necessary signed informed consent from the pregnant female partner directly, the Investigator will record pregnancy information on the appropriate form and submit it to the Sponsor within 24 hours of learning of the partner's pregnancy. The female partner will also be followed to determine the outcome of the pregnancy. Information on the status of the mother and child will be forwarded to the Sponsor. Generally, the follow-up will be no longer than 6 to 8 weeks following the estimated delivery date. Any termination of the pregnancy will be reported regardless of fetal status (presence or absence of anomalies) or indication for the procedure.

Female subjects who become pregnant

- Female subjects who become pregnant should discontinue treatment and be withdrawn from the study.
- The Investigator will collect pregnancy information on any female subject who becomes pregnant while participating in this study. Information will be recorded on the appropriate form and submitted to the Sponsor within 24 hours of learning of a subject's pregnancy.
- The subject will be followed to determine the outcome of the pregnancy. The Investigator will collect follow-up information on the subject and the neonate and the information will be forwarded to the Sponsor. Generally, follow-up will not be required for longer than 6 to 8 weeks beyond the estimated delivery date. Any termination of pregnancy will be reported, regardless of fetal status (presence or absence of anomalies) or indication for the procedure.
- While pregnancy itself is not considered to be an AE or SAE, any pregnancy complication or elective termination of a pregnancy will be reported as an AE or SAE. A spontaneous abortion is always considered to be an SAE and will be reported as such. Any post-study pregnancy related SAE considered reasonably related to the IP by the Investigator will be reported to the Sponsor as described in Section 8.3.4. While the Investigator is not obligated to actively seek this information in former study subjects, he or she may learn of an SAE through spontaneous reporting.

